2.6. Recruitment

The study employs convenience sampling. Recruitment will take place through email to families who receive care at HWNV in English and Spanish as well as posters advertising the program placed in community spaces where children and families who are clients at HWNV spend time (updated recruitment flyer, Appendix B). If guardians are interested in being part of the program, there will be a contact person listed on the advertisement who will screen for eligibility. If a family is screened as eligible to be part of the x-IHPC intervention, a member of the study team will meet with the family virtually or in person and consent the guardian to be part of the study. This consent process will take place with a trained interpreter. The consent will be emailed to program participants prior to the consent conversation when possible. Whether consent occurs virtually or in person, a hard copy of the consent will be printed and stored by the Inova PI. A copy of the consent will be given to the guardian.

Participants will also be screened for eligibility during their well-child clinic visit at HWNV by the physician study PI. If guardian meets the study inclusion criteria, the PI will introduce the study to the guardian and ask if they would like more information.

Families will decide if they have the capacity to participate in the x-HPC intervention. They will be offered both groups, but can choose which group works for their family. We realize that this introduces selection bias into the study (families who self select to be part of the intervention are families who are interested in health and have the time and ability to attend). However, the intervention takes a lot of time and families need to choose the arm that works for their schedule.

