2.7. Inclusion Criteria

Inclusion criteria include:

1. Child and Parent are clients at HealthWorks for Northern Virginia
2. Child between the ages 6-12 years
3. Child has a BMI percentage greater than 85%
4. Primary parent or guardian is > 18 years of age
5. Family identifies as Hispanic and Spanish is one of the primary languages spoken in the home
6. Children will be living with the primary guardian or parent for the duration of the program
7. Access to the internet
8. Parent or guardian is willing to commit to engaging in the 12 week program

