3.4. Endpoints/Outcomes Measurements

3.4.1. Primary outcomes.

3.4.2.

Primary outcomes measured via a survey, which will include food frequency questionnaires, screen time estimates, physical activity questionnaires, estimated screen time reports, and guardian self-efficacy and confidence questions related to modifiable lifestyle behaviors.^{15 16 17} Survey data will be collected during phone calls from the PI or CHW at the outset of the study and then again at the conclusion of the study. An example survey has been included (Appendix C: Survey). The survey questions may be altered or deleted based on feedback from the study advisory board or the CHWs, as this study is based on community engagement and feedback. The final survey instrument will be submitted to this IRB for approval before the data collection begins.

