3.5. Consent/Accent

Once a guardian has been screened as eligible for inclusion in the study, they will be approached by the physician PI and asked if they are interested in being part of the study. If they are interested, the PI will discuss whether they are interested in joining the comparison group or the intervention group. A member of the study team will meet with the family virtually or in person and consent the guardian to be part of the study (Appendix D: Consent). This consent process will take place with a trained interpreter. The consent will be provided in both English and Spanish. The consent will be emailed to program participants prior to the

¹⁵ Bryant, M. J., Ward, D. S., Hales, D., Vaughn, A., Tabak, R. G., & Stevens, J. (2008). Reliability and validity of the Healthy Home Survey: a tool to measure factors within homes hypothesized to relate to overweight in children. *The international journal of behavioral nutrition and physical activity*, 5, 23. <https://doi.org/10.1186/1479-5868-5-23>

¹⁶ Schrempf, S., van Jaarsveld, C. H., Fisher, A., & Wardle, J. (2015). The Obesogenic Quality of the Home Environment: Associations with Diet, Physical Activity, TV Viewing, and BMI in Preschool Children. *PloS one*, 10(8), e0134490. <https://doi.org/10.1371/journal.pone.0134490>

¹⁷ Kininmonth, A. R., Schrempf, S., Smith, A., Dye, L., Lawton, C., Fisher, A., Llewellyn, C., & Fildes, A. (2021). The Home Environment Interview and associations with energy balance behaviours and body weight in school-aged children - a feasibility, reliability, and validity study. *The international journal of behavioral nutrition and physical activity*, 18(1), 167. <https://doi.org/10.1186/s12966-021-01235-3>

consent conversation when possible. Whether consent occurs virtually or in person, a hard copy of the consent will be printed and stored by the Inova PI. A copy of the consent will be given to the guardian.

3.6. Monitoring Subjects and Criteria for Withdrawal of Subjects from the Study.

Study participants may leave the study at any time, without penalty. In some cases, the participant may be withdrawn if the HWNV physician PI determines that the study intervention is too burdensome for the participant or is adversely affecting the study participant's health. If any study participant leaves the study or is withdrawn from the study, their data will not be used in analysis.

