4.2. Method of Data Analysis

Analyses will follow the intention-to-treat principle, which categorizes participants by their treatment assignments regardless of adherence to the intervention or incomplete follow-up, and includes them in all analyses. Descriptive statistics will be calculated and reported as mean, standard deviation and 95% confidence intervals for continuous variables and frequency and percentage for categorical variables. Characteristics of study participants will be compared at baseline between the intervention and control groups and tested for significance using the two-sample t-test for continuous variables and the Chi-square test for categorical variables. Comparisons that are significant at the $P<0.10$ level will be considered for inclusion in multivariable models for primary and secondary analyses given that participants will not be randomized to their respective treatment groups.

Primary analyses will examine diet quality, screen time, physical activity, and guardian self-efficacy and confidence of those in the intervention and control groups while controlling for the correlated nature of the repeated measures within participants (i.e. baseline, post-intervention, and 6-month post-intervention). Secondary analyses will compare the BMI of guardians and BMI percentile of children at the three time points between the intervention and control groups. A longitudinal data analysis strategy will be employed with generalized estimating equations with robust CIs for both primary and secondary outcomes (Albert, 1999; Ma et al., 2012). A 2-sided p-value <0.05 will be accepted to indicate statistical significance. Additional analyses will be conducted to determine if results were influenced by other covariates including demographics (age, gender, educational attainment of guardian, income, etc.). All analyses will be conducted in SAS version 9.2.

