Appendix C: Study Survey

Script and procedures for administration of the Buen Provecho! Study Survey

Adapted with permission from: Bryant, M. J., Ward, D. S., Hales, D., Vaughn, A., Tabak, R. G., & Stevens, J. (2008). Reliability and validity of the Healthy Home Survey: a tool to measure factors within homes hypothesized to relate to overweight in children. *The international journal of behavioral nutrition and physical activity*, 5, 23. <https://doi.org/10.1186/1479-5868-5-23>

The script

Administered By:

Date:

Start Time:

CALL PARTICIPANT

Good morning/evening. This is <your name>from <institute name>. Could I please speak to <participant name>?

Hello <participant name>. We have received the form that you mailed to us with consent to take part in our family home study. As we described in the consent form, the first part of the study involves a telephone interview which should take approximately 15 minutes. Is now a good time to conduct that interview with you?

If no *No problem. I will try again using another time that you suggested might be alright on your availability form. Thank you. Goodbye.*

If yes..... *Okay. I'll begin with a few general questions and then move on to more specific questions about your family home environment. Please feel free to stop me at any point or ask me to clarify any questions that you don't understand. There are no right or wrong answers. Please answer honestly. You are not being judged on any of your responses.*

What is your name?

* must provide value

What is your gender?

What is your ethnicity?

Hispanic or Latino - a person of Cuban, Mexican, Puerto Rican, South or Central American, or other Spanish culture or origin, regardless of race.
 Not Hispanic or Latino

What is your race?

American Indian
 Asian
 Hawaiian
 Black or African American
 White
 More than one race

What is your child's name?

* must provide value

What is your child's age?

* must provide value

What is your child's gender?

* must provide value

Are you the primary caregiver for < child's name> that you indicated as being suitable for this study?

* must provide value

Yes
 No

reset

What is your relationship with < child's name>?

How many adults older than 17 years live in your home?

* must provide value

Only include people who live in your home all of the time.

How many children under the age of 18 years live in your home?

Only include people who live in your home all of the time.

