During the last 7 days, on how many days did < child> walk for at least 10 minutes at a time?	
How much water does your child drink each day?	
Do you feel that you need to change the amount of fruits and vegetables your child eats each week?	
How confident do you feel that you can increase the number of vegetables your child eats each week?	
How confident do you feel that you can obtain fresh fruit and vegetables for your family to eat during the week?	
How confident do you feel that you can cook healthy meals for your family?	
Do you feel that you need to change the amount of time your child spends using screens?	

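### The plan names interest in health and time to attend as what drives arm choice, but shows no direct measure of time, only post-choice proxies for interest, and neither as a covariate, so 4.2 can adjust for the admitted bias only in part

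*Combined protocol and SAP*

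**What the plan says.** Allocation is by family choice. Section 3.3 gives no randomization, and Section 2.6 (repeated in 3.1) says of families: "They will be offered both groups, but can choose which group works for their family". The same paragraph concedes selection bias and states its source: those who choose the intervention are "families who are interested in health and have the time and ability to attend".

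On timing, Section 3.5 has the physician investigator raise the arms with each interested guardian ("the PI will discuss whether they are interested in joining the comparison group or the intervention group") and then describes the consent meeting. Section 3.4 states: "Survey data will be collected during phone calls from the PI or CHW at the outset of the study and then again at the conclusion". The Appendix C script opens with "We have received the form that you mailed to us with consent to take part in our family home study", so the baseline survey follows consent and hence follows the discussion of arms.

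On content, the survey as shown has nothing on work hours, schedule or time to attend. Its nearest items to interest are two need-to-change questions, one on screens and one reading "Do you feel that you need to change the amount of fruits and vegetables your child eats each week", and three guardian confidence questions.

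On analysis, Section 4.2 considers for the models any baseline characteristic that differs between arms at P<0.10, and gives non-randomization as the reason. It adds analyses of other covariates, including "demographics (age, gender, educational attainment of guardian, income, etc". Neither stated driver of choice is named.

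Inclusion criterion 8 in Section 2.7 reads "Parent or guardian is willing to commit to engaging in the 12 week program". As written it applies to every family in either arm.

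**The concern.** The protocol identifies its own confounders and then does not plan to measure them directly. Interest in the child's health and free time could each plausibly change diet, screen use and activity at home without any program. Adjusting for age, gender, education or income removes only the part of that influence that runs through those variables.

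If the x-IHPC arm improves more, a reader can say that keener families with more time would have improved anyway, and the data would give only a weak answer. The state of each family before it chooses cannot be recovered later.

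**Working it through.** **1. The plan's own figure.** Section 4.1 gives 25 per arm (n=50) without power, effect size, SD or dropout, so it cannot be reproduced. It is used below only as the planned size.

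**2. Where each driver could enter the model.**

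| Source | Time to attend | Interest in health |
|---|---|---|
| Criterion 8 (2.7) | Same for all enrolled families; no variation | Same for all enrolled families; no variation |
| Appendix C, baseline | No direct item; household composition only | Need-to-change and confidence items, after the arm discussion |
| 4.2, named covariates | Not named | Not named |
| 4.2, P<0.10 rule | Nothing direct to screen | Proxies, if they pass |

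The confidence items are also part of a primary outcome (3.4), so at baseline they serve both as an outcome value and as a proxy for interest.

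**3. How often the P<0.10 screen would flag a real imbalance.** Inputs: 25 per arm and two-sided 0.10 (4.2); the true imbalance d is assumed. A two-sample t-test has 48 df, critical value 1.677 and noncentrality d × sqrt(25/2). For d = 0.5 this is 0.5 × 3.536 = 1.768.

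| True imbalance (SD) | Chance of being flagged |
|---|---|
| 0.2 | 18% |
| 0.3 | 28% |
| 0.5 | 54% |
| 0.8 | 87% |

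A flagged variable is then only considered for inclusion, so these are upper limits on the chance that it enters the model by this route.

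**4. Illustrative size of the bias.** Neither input is in the documents. Assume that the arms differ by 0.5 to 1.0 SD on a driver and that the driver correlates 0.2 to 0.3 with outcome change.

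- Bias = imbalance × correlation: 0.5 × 0.2 = 0.10 SD, up to 1.0 × 0.3 = 0.30 SD.
- SE of the arm difference = sqrt(2/25) = 0.283 SD of the analysed change.
- Rejection rate at two-sided 0.05 with no true effect (noncentral t, 48 df, noncentrality = bias/0.283): 6.4% at 0.10, 10.7% at 0.20 and 18.0% at 0.30.

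**5. What a proxy achieves.** If a proxy equals the driver plus independent noise, with reliability 0.5 (assumed), the remaining bias is bias × (1 − 0.5). A bias of 0.20 falls to 0.10 SD (10.7% to 6.4%), and 0.30 falls to 0.15 SD (18.0% to 8.1%). Adjustment by proxy reduces the bias without removing it.

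**6. Precision cost of pre-specifying a driver.** With equal arms that differ by d SD on a covariate, the variance of the arm effect is inflated by about 1 + d²/4: 1.06 at d = 0.5 and 1.25 at d = 1.0, per covariate. This is before any gain from explained outcome variance.

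**The case against.** The strongest reply is that 4.2 is not silent. Its P<0.10 rule is aimed at non-randomization, its covariate list is open-ended, and baseline outcome values are among the repeated measures. A reader might infer from the missing items that no model in 4.2 can adjust for the bias. The documents do not support that, because partial adjustment by proxy is possible, at least for interest.

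A reader might also infer that neither driver is recorded in any form, or that only a measure taken before the choice is valid. Neither follows. A confounder has to be measured before the intervention, and a baseline survey taken after the choice can still supply one. The caution is that having chosen may colour the answers. Criterion 8 does screen willingness at eligibility. Because every enrolled family must meet it, it cannot serve as a covariate. If it is enforced in both arms, the real imbalance may be smaller than assumed above.

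The survey is also provisional. Section 3.4 calls it an example that may change before IRB approval, and the text available may not show every item or response option. The script mentions an availability form, but only for timing the call. The absence of a time item is therefore a statement about the survey as shown.

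Finally, this is a pilot that discloses the bias twice, and the magnitude rests on assumed inputs. At the low end, 6.4% is barely above 5%.

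What remains after all this is that no direct measure of time to attend is shown, interest has only proxies, and neither is named for adjustment.

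**Conclusion.** The point holds in limited form. The plan admits a specific selection bias but, on the survey as shown, can adjust for it only partly. For interest, adjustment depends on proxies passing a screen that flags a true 0.5 SD imbalance about 54% of the time. For time to attend there is no direct variable to screen.

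The false-positive range of 6.4% to 18.0% is an illustration. It rests on an assumed 0.5 to 1.0 SD imbalance, an assumed correlation of 0.2 to 0.3, no adjustment, and all 25 per arm analysed. The documents give no basis for narrowing it. The change is worth making, with medium confidence, because it is cheap and the survey is still open to revision.

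**What to change.** **Sections 2.6 and 3.5.** Before the arms are discussed, ask every family at screening two fixed questions: how many hours or evenings a week are free for a class, and, from 0 to 10, how important changing the child's habits is now. After the choice, record the main reason for it.

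**Section 2.7.** Reconcile criterion 8 with the family choice described in 2.6.

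**Section 4.2.** Pre-specify available time and importance as covariates in the primary model whatever their baseline P values. Include their interactions with time: baseline is itself one of the repeated measures, so a main effect alone shifts all time points together and would leave an arm-by-time contrast essentially unchanged. Report the result as an adjusted association with residual confounding.

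**What to leave out of the model.** Report any stated preference and the reason for choice descriptively. Preference nearly determines arm, so forcing it in risks poor overlap. A comparison limited to families who chose counseling for schedule reasons should also be descriptive. If 5 to 12 such families were set against 25, the difference detectable with 80% power would be about 2.80 × sqrt(1/5 + 1/25) = 1.4 SD to 2.80 × sqrt(1/12 + 1/25) = 1.0 SD.

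**Cost.** About two minutes per family and protocol, SAP and IRB wording. The model gains two main effects plus two interaction terms with the two survey points in 3.4, or four with the three time points in 4.2, at n=50. Variance inflation is roughly 1.06 to 1.25 per covariate. Single-item measures will leave some confounding in place.

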2.7. Inclusion Criteria

Inclusion criteria include:

1. Child and Parent are clients at HealthWorks for Northern Virginia
2. Child between the ages 6-12 years
3. Child has a BMI percentage greater than 85%
4. Primary parent or guardian is > 18 years of age
5. Family identifies as Hispanic and Spanish is one of the primary languages spoken in the home
6. Children will be living with the primary guardian or parent for the duration of the program
7. Access to the internet
8. Parent or guardian is willing to commit to engaging in the 12 week program

2.8. Exclusion Criteria

Exclusion criteria include:

1. Family plans to change location within the year
2. During initial screening for the study, the study PI determines that the intervention may exacerbate existing medical conditions of the child or the family.

3. STUDY METHODS AND PROCEDURES

3.1. Study Treatment/Intervention

The purpose of this community-engaged quasi-experimental study is to determine whether family-based, culturally tailored, virtual intervention enables and motivates parents and children (experimental group) to shape the weight-related aspects of their home environments and lifestyle behavioral practices (diet, exercise, screen behaviors) to be more supportive of their family's optimal health and weight, compared to standard in-office counseling (comparison group).

Intervention: This project builds on the success of an existing community-focused program called the IHPC. Within the Inova Division of Population Health the IHPC aims to reduce obesity among low-income children and prevent the future occurrence of heart disease/stroke, Type 2 Diabetes, and other related diseases. To date, IHPC has engaged more than 1,200 children in Northern Virginia in healthy-eating interventions. Currently, this popular program is delivered in English, for 5-8 weeks, to children grades K - 8 in an afterschool setting.

The proposed study will examine the effectiveness of an expanded IHPC (x-IHPC), which will be virtual, family-based, and specifically designed for low income Hispanic families in our community; all of which are evidence-based strategies for enhancing healthy eating interventions. Family-based interventions are not a novel approach to obesity reduction. Two decades of research shows that family-based interventions work better than individual interventions at reducing childhood obesity.^{13,14} When the IHPC moved to a virtual format due to COVID-19 in 2020, facilitators required parental home involvement. The anecdotal success of that family involvement has fueled the desire of IHPC to expand their programming to include more education and activities for parents.

The x-IHPC will include 4 extra modules, (= 4 additional weeks of programming) that will be developed by a dietitian curriculum specialist. The expanded IHPC will also include programming just for parents to increase their involvement. A key pillar of this study is identifying and training CHWs from HWNV to be Spanish-language facilitators of x-IHPC. Training these CHWs and including them in designing the x-IHPC curriculum will ensure that the programming is culturally appropriate; includes local features that relate directly to the community's needs; and enables facilitators to respond effectively to the questions and learning needs of the parents and children involved in the program.

IHPC provides produce boxes, nutrition and meal-preparation, education, and supportive counseling to address barriers related to obtaining produce and food. The intervention provides participants with a bi-weekly produce box for 12 weeks (6 boxes total) and helps families identify sustainable ways to obtain vegetables once the produce boxes end. Providing produce boxes exposes families to new, unfamiliar vegetables that are not common in their home countries, and allows families to experiment with new recipes on a limited income. The CHW will support families by coaching them on how to prepare these unfamiliar vegetables, give tips on finding sales at grocery stores, as well as by navigation to food assistance sites including food pantries, school meal sites and bus routes, and neighborhood food distributions. Parents will learn strategies to increase vegetable consumption by addressing perceived

barriers – such as the child doesn't like vegetables. Curriculum will also include topics such as how to increase physical activity and reduce screen time. Both the families in the x-HPC and families who receive the in-office counseling will be offered the 6 vegetable food boxes, delivered on a bi-weekly basis during their time in the study.

Families will decide if they have the capacity to participate in the x-HPC intervention. They will be offered both groups, but can choose which group works for their family. We realize that this introduces selection bias into the study (families who self select to be part of the intervention are families who are interested in health and have the time and ability to attend). However, the intervention takes a lot of time and families need to choose the arm that works for their schedule.

